Objectives	 To set-up an international European electronic registry of patients with idiosyncratic DILI, (iDILI) enrolled prospectively with the collation of indepth phenotyping: including details of drug dose, duration, concomitant medications, host demography, comorbidity including insulin sensitivity as well as the course of the event. To collect and store biological samples (blood, urine, stool and liver biopsy) from patients with suspected idiosyncratic DILI and the symptomatic non-DILI control group through the course (at onset and follow-up) of the event. To collect and store biological samples (blood, urine and stool) from control patients at a single visit. To make biosamples available for collaborative research through a dedicated biobank. To determine and analyse individual phenotypes and biochemical and cellular component levels in patients and control groups in order to develop translatable disease biomarkers
Study Configuration	Case controlled multi-centre study for the collection, analysis and storage of biological samples and data (medical, demographic and clinical).
Setting	Secondary care (hospital based)
Sample size estimate	N/A
Number of participants	 UK cohort: 150 suspected DILI cases (symptomatic) 20 cases of autoimmune hepatitis with DILI-like symptoms* Total, including European cohort: 300 confirmed DILI cases (50 in the UK)
	diagnosis).

Description of interventions	DILI patients, symptomatic non-DILI patients: Blood, urine and stool samples will be collected at each visit.
	We plan to additionally collect any available surplus liver biopsy or blood samples taken as part of clinical care (and any archived paraffin sections taken previously as part of clinical care).
Duration of study	Recruitment will be over a 9 year period (to Apr 2024)

INTRODUCTION

Background

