Causal DILI agents will be classified according to World Health Organisation (WHO) anatomical therapeutic chemical (ATC) classification system. Associated diseases will be classified according to the WHO tenth edition of the international classification of diseases, ICD-10.

STUDY POPULATION

Recruitment will be over a nine year period (up to April 2024).

-For suspected DILI patients : 3-7 visits, (each visit lasting for up to 30mins). Each patient will be in the study for up to 6 months duration.

Follow-up: Each patient will have a clinical follow up until the event resolves or 12 weeks after the first event whichever occurs later. We will also follow-up outcomes in clinical notes over a 10 year period after recruitment where consent is given.

Enrolment:

We expect to enrol each case at the earliest opportunity possible, following the suspected DILI event (or AIH event) (up to a maximum of 8 weeks from diagnosis) when research team anticipates that they will meet inclusion criteria below. Each patient will be followed from the identification of hepatotoxicity until normalization of the analytical liver profile.

Enrolment will begin once a patient has been clinically diagnosed with suspected DILI and gives consent to take part in the study. In all instances the visit schedule should be adapted to routine hospital procedures in order to facilitate patient participation as well as avoid additional hospital costs (see diagram below).

- Control participants (on medication or untreated but without DILI symptoms): A

single study visit of up to 30 minutes duration. Controls will be required to provide biological samples, demographic and medical data will also be collected.

Study Duration:

Enrolment will end at 9 years from the start of the study (Apr 2024) or once the recruitment target has been met, whichever is soonest.

INCLUSION CRITERIA

All patient and control groups:

- Aged 18 years and over
- Able to give written informed consent OR consent provided by consultee (personal or nominated) for potential participants with suspected DILI who lack capacity to give written informed consent.

A. Suspected DILI Patients:

Adults diagnosed with suspected acute DILI (within 8 weeks of diagnosis) and meeting the following criteria will be included:

1. Meets one of the following analytical thresholds at enrolment (visit 1)

- alanine transaminase (ALT) exceeding 5 times upper limit of normal (ULN) OR
- alkaline phosphatase exceeding 2 times ULN OR

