- ALT exceeding 3 times ULN plus bilirubin exceeding 2 times ULN

Patients who are found to not meet these thresholds on date of recruitment when clinical test results are returned should not be invited for subsequent visits.

2. Exposure to drugs including any prescription drug, over-the-counter drug, recreational drug, herbal remedies or dietary supplements prior to the DILI onset.

Pro-Euro-DILI Registry Protocol Page 13 of 32

3. Clinical suspicion of having possible DILI.

EXCLUSION CRITERIA

Anyone with any definite diagnosis of the following conditions **identified prior to recruitment** will not be included in the study as a suspected DILI case:

- Acute viral hepatitis due to hepatitis A, B, C, E, CMV, EBV, HIV.
- Acute presentation of auto-immune hepatitis unrelated to the drug.
- Confirmed acute liver injury that explains the clinical manifestation e: ischemic hepatitis, acute ascending cholangitis.
- Acute exacerbation/ decompensation of known chronic liver disease that explains the acute event.
- Biliary obstruction explaining cholestasis.
- On the judgement of CI that the person has certain alternative explanation to the acute event (rather than DILI).

It is possible that detailed investigations of suspected DILI cases my reveal one or more of these conditions, this will not exclude the participants from continuation with study visits but these cases will be adjudicated as 'non-DILI' and analysed as a separate study group.

WITHDRAWAL CRITERIA

It will be explained to the potential participant that entry into the study is entirely voluntary and that their treatment and care will not be affected by their decision. It will also be explained that they can withdraw at any time from the study but attempts will be made to avoid this occurrence. In the event of their withdrawal it will be explained that their data collected so far cannot be erased and we may still use the anonymised data in the final analyses. Remaining tissue samples can be destroyed/disposed of if the participant so wishes. Similarly, the information about them will be deleted so that it cannot be used again. We will explain to the participant that if they decide to withdraw after a long period of time, the samples may already have been used and we cannot recall samples or information from researchers if this is the case.

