The Principal Investigator may also remove a subject if, in his / her opinion, it is in the best interests of the subject. If a patient permanently withdraws from the study, or is lost to follow-up, the reason will be recorded.

PARTICIPANT SELECTION AND ENROLMENT

IDENTIFYING PARTICIPANTS

Potential participants will be recruited from a secondary care setting, from the acute and inpatient services as well as outpatient clinics at the treating hospital. Patients who may have DILI event or auto- immune hepatitis will be identified and approached. The initial approach will be from a member of the patient's usual care team (which may include the investigator and his research team), and information about the study will be on display in the relevant clinical areas (A study Info leaflet for patients and study info poster for clinicians are provided as separated files).

Patients will be identified as having suspected DILI from their medical records and laboratory test results from samples taken as part of their standard clinical care. The study will be explained and potential participants will be given a copy of the Participant Information Sheet Pro-Euro-DILI Registry Protocol Page **14** of **32**

to read and asked if they would be interested in taking part in the study. Invitation letters will also be sent out to potential participants with their results letter and or clinic appointment letter.

If a patient agrees to take part in the study, they will be asked to sign a copy of the consent form. Once signed, the patient will have a blood sample taken, the results of this blood test taken at enrolment will be used to assess/determine eligibility for subsequent visits; if eligible, the patient will continue in the study. In all instances the visit schedule should be adapted to routine hospital procedures in order to facilitate patient participation as well as avoid additional hospital costs.

The investigator or their nominee, e.g. from the research team or a member of the participant's usual care team, will inform the participant (or their nominated representative if they are unable to give informed written consent) of all aspects pertaining to participation in the study.

If needed, the usual hospital interpreter and translator services will be available to assist with discussion of the trial, the participant information sheets, and consent forms, but the consent forms and information sheets for UK sites will not be available printed in other languages.

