Healthy Control Group:

Adults who are exposed to the same drugs (as those responsible for DILI) without developing DILI will be identified. The Chief Investigator will access hospital pharmacy databases to identify patients taking specific drugs of interest. Then patients exposed to particular drugs without developing DILI will be invited to participate in the study as a control group. In the UK this will be done at the Nottingham site initially, extending to other sites where appropriate.

We will also advertise through BRC website (https://nddcbru.org.uk/pro-euro-dili) (appendix 2 shows screen shot) and social media pages (Facebook and Twitter) to invite people who have taken the particular drugs to contact us if they are interested in participating in the study (as control group).

A proportion of patients who are suspected to have DILI and enrolled as cases will be found to have an alternative explanation for their clinical manifestation found on subsequent investigation. The data and samples taken from these patients will be retained in the study and termed 'symptomatic controls' for analysis purposes. Sample and data collection will be continued in line with confirmed DILI participants.

INFORMED CONSENT

The process for obtaining participant informed consent will be in accordance with the REC guidance, and Good Clinical Practice (GCP) and any other regulatory requirements that might be introduced. Since DILI symptoms are acute and patients often present in emergency departments with sudden onset of severe symptoms, a long period (e.g. 24h) to consider consent is often difficult to provide in order to recruit patients while symptomatic and without asking patients to make additional hospital visits. Therefore, where appropriate, patients will be given a reasonable time period (ideally1 hour without disturbance), to read the patient information sheet and consider enrolment before being approached for consent by the research team. Appropriate steps will be taken to ensure that the patient is able to discuss participation in the study with those not involved in the research. The investigator or

Pro-Euro-DILI Registry Protocol Page 15 of 32

their nominee and the participant or other legally authorised representative shall both sign and date the Consent Form before the person can participate in the study.

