If the PI or Investigator and research team are unable to identify/appoint a suitable personal consultee then efforts will be made to nominate a health professional who is unconnected with the research project to act as a professional consultee. We will firstly ask a member of the standard medical care team of the person who lacks capacity if they would consider taking on the role. The professional consultee will be required to perform the same role as a personal consultee in advising the research team but they may not know the person who lacks capacity and therefore may be required when attempting to determine what the person's wishes and feelings about the research would be if they had capacity, seek the views of any family, friends/carers of the person who lacks consent, or seek other

professional colleagues with an interest in the person's welfare or condition. We will continue to assess capacity throughout the research and will seek consent as soon as feasible.

All consultees (personal and professional) will receive a copy of the consultee information sheet to read. If and when the participant regains capacity, consent will be sought from the participant retrospectively, and will be withdrawn from the study if consent is not given.

We currently have no sites or plans to recruit from sites in Northern Ireland. If this was to occur, we are aware that Northern Ireland follow different legislation and a different process would need to be followed regarding the documentation. We would ensure that this process was followed correctly. We are currently seeking approval to recruit these patients in England and Wales only. We plan to put a future application to a Scotland A REC in order to allow us to recruit patients who lack capacity in Scotland.

STUDY PROCEDURES

SAMPLE COLLECTION Suspected DILI patients

Biological samples will be collected from each enrolled patient on up to 7 occasions (see diagram below). These visits will take place as soon as possible following acute presentation; there will be a time lag of up to 8 weeks between identification of an episode of DILI by the team responsible for the clinical care of the patients and the patient giving consent to take part in the study. Patients' blood tests must meet the eligibility inclusion criteria on the day they are enrolled (Day 0, visit 1) in order to continue to participate in the study.

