All routine laboratory analysis will be done by appropriate hospital as part as normal patient care. Blood will be processed for storage of serum and plasma as outlined in the SOP. Data and all appropriate documentation will be stored for a minimum of 25 years after the completion of the study, including the follow-up period.

We will collate detailed and comprehensive data using an electronic case report form (eCRF) to achieve in-depth phenotyping.

The procedure for data removal in the event of withdrawal of consent is described on pg 25.

Statistical Analyses

Researchers will be blinded to patient type/group being investigated – samples will be anonymized and labelled only with study ID code. Study groups will be compared using T-tests and non-parametric testing to identify biomarkers which distinguish DILI.

STUDY MANAGEMENT

The day-to-day management of the study will be co-ordinated through Nottingham Digestive Diseases Centre and NIHR Nottingham Biomedical Research Centre.

SPONSOR

Nottingham University Hospitals NHS Trust will act as the main sponsor for UK based sites for this study. Delegated responsibilities will be assigned to the NHS trusts taking part in this study.

FUNDING

Participant stipends and payments

Participants will not be paid to participate in the study. Travel expenses will be offered for any hospital visits in excess of usual care.

AUDITS

The study may be subject to inspection and audit by Nottingham University Hospitals under their remit as sponsor and other regulatory bodies to ensure adherence to GCP and the NHS Research Governance Framework for Health and Social Care (2nd edition).

STUDY CONDUCT

Study conduct will be subject to systems audit for inclusion of essential documents; permissions to conduct the study; CVs of study staff and training received; local document control procedures; consent procedures and recruitment logs; adherence to procedures defined in the protocol (e.g. inclusion / exclusion criteria, timeliness of visits); accountability of study materials and equipment calibration logs.

STUDY DATA

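### Symptomatic controls found through later work-up are likely to be sampled earlier in their injury than confirmed DILI cases, and the stated marker comparison takes no account of time since onset

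*Protocol*

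**What the plan says.** - **Entry window.** Inclusion Criteria, section A: "Adults diagnosed with suspected acute DILI (within 8 weeks of diagnosis) and meeting the following criteria will be included". Sample Collection describes the same interval as a lag before consent: "there will be a time lag of up to 8 weeks between identification of an episode of DILI by the team responsible".
- **Bar on entry.** Exclusion Criteria: a person with a definite listed diagnosis made before recruitment "will not be included in the study as a suspected DILI case". The last item extends this to any alternative explanation that the chief investigator judges certain.
- **Source of symptomatic controls.** Identifying Participants, under Healthy Control Group: a proportion of suspected patients "enrolled as cases will be found to have an alternative explanation for their clinical manifestation found on subsequent investigation". They are kept, relabelled as symptomatic controls, and sampled like the confirmed cases.
- **Autoimmune hepatitis (AIH).** The Study Summary plans "20 cases of autoimmune hepatitis with DILI-like symptoms" in the UK, listed apart from the 150 suspected cases. Identifying Participants says "Patients who may have DILI event or auto- immune hepatitis will be identified and approached". Enrolment gives them the same limit: "following the suspected DILI event (or AIH event) (up to a maximum of 8 weeks from diagnosis".
- **Clock.** Sample Collection sets Visit 1 as Day 0, times Visits 2 and 3 from it, and requires the blood tests to meet the inclusion thresholds on that day.
- **Analysis.** Statistical Analyses: "Study groups will be compared using T-tests and non-parametric testing to identify biomarkers which distinguish DILI". Time since onset is not mentioned.

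**The concern.** The nominal window is the same for every suspected case, but it does not stay open equally long. For a look-alike patient it shuts on the day the viral screen, autoantibodies, imaging or clinical judgement settles the cause. For a DILI patient nothing comparable shuts it. Late entrants are therefore increasingly DILI patients, plus look-alikes whose work-up is slow.

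The protocol accepts that the injury changes with time. It follows patients to normalisation of the liver profile, and its adverse event section notes that injury can go on worsening after the drug is withdrawn. If the groups are sampled at different phases, a marker of phase can pass for a marker of cause. A true DILI marker that fades can equally be hidden. The symptomatic controls are where this matters, because drug-exposed people without liver injury cannot show whether a marker separates DILI from other acute liver injury.

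**Working it through.** The protocol gives its sample size estimate as not applicable and states no power, effect size or SD, so there is no figure to reproduce.

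**Step 1: direction, from the rules alone.** Let T be the day of entry, counted from identification of the episode, and D the day an alternative cause becomes definite.
- DILI patient: eligible if T ≤ 56 days.
- Look-alike: eligible as a suspected case if T ≤ 56 days and T < D.

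If both kinds of patient come forward with the same timing, the extra condition can only shorten T among the look-alikes. No assumption about marker kinetics is needed for this.

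**Step 2: group sizes.** The Primary endpoint gives 430 suspected and 300 confirmed cases, so at most 430 − 300 = 130 are symptomatic non-DILI patients.

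**Step 3: what a pure phase shift does.** Suppose cause has no effect and phase moves the mean by d SD. At an assumed two-sided 5% level:
- SE = √(1/130 + 1/300) = 0.105
- chance of significance in the direction of the shift = Φ(d/0.105 − 1.96)

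| d (SD) | 0.1 | 0.2 | 0.3 | 0.5 |
|---|---|---|---|---|
| Chance | 0.16 | 0.48 | 0.82 | 0.997 |

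**Step 4: how large d might be.** This is a simulation of 1,000,000 patients per scenario. Every kinetic input is an assumption:
- entry even over days 0–56, or weighted early (mean about 13 days);
- exponential time to alternative diagnosis, mean 7, 14 or 28 days;
- marker with log-SD 1, decaying with a half-life of 7, 14 or 28 days and independent of ALT;
- ALT at day 0 with median 15 × ULN and log-SD 0.8, half-life 14 days;
- the same entry rule, ALT above 5 × ULN, applied to both groups.

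The last three columns show the shift in SD, with the chance of significance in brackets.

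| Entry | Mean days to alternative diagnosis | Mean entry day, DILI v non-DILI | Half-life 7 d | Half-life 14 d | Half-life 28 d |
|---|---|---|---|---|---|
| Even | 7 | 16.1 v 5.8–5.9 | 0.75 (1.00) | 0.46 (0.99) | 0.25 (0.66) |
| Even | 14 | 16.1 v 9.1 | 0.49 (1.00) | 0.31 (0.84) | 0.17 (0.37) |
| Even | 28 | 16.1 v 11.9 | 0.28 (0.77) | 0.18 (0.42) | 0.10 (0.16) |
| Early | 7 | 9.2 v 4.2–4.3 | 0.41 (0.97) | 0.23 (0.60) | 0.12 (0.20) |
| Early | 14 | 9.2 v 5.9 | 0.27 (0.72) | 0.15 (0.31) | 0.08 (0.11) |
| Early | 28 | 9.2 v 7.2 | 0.16 (0.32) | 0.09 (0.13) | 0.05 (0.06) |

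The threshold matters. Without it, the mean entry days under even entry would be 28.0 against 7.0–19.3. It narrows the gap in every scenario and closes it in none. The ALP and the ALT-plus-bilirubin routes to eligibility were not modelled.

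**The case against.** **The design itself is sound.** Enrolling on suspicion and adjudicating later is a reasonable way to build a diagnostic-marker cohort. Both groups share the threshold, the visits and the follow-up. This stands, and the point does not ask for any entry rule to change.

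**Work-up may finish only after entry.** Appendix 1 places the viral screen, autoantibodies and ultrasound at Visit 1, where clinically appropriate, and only a definite diagnosis bars entry. Many look-alikes will still be unresolved when they consent. This limits the size (compare the 28-day rows) but does not reverse the direction.

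**The gap may be trivial.** Enrolment is to be as early as possible. A marker that tracks ALT would also differ less than the simulated one, because late entrants who still pass the threshold tend to be those with high peaks. This stands: the lowest scenario is close to no bias.

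**A statistical analysis plan could adjust.** Only the protocol is available here, and its single sentence does not forbid covariates. This also stands as a limit. But the imbalance comes from the protocol's own entry rules, and any adjustment needs onset dates in both groups.

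**Stronger readings the text does not support.** A reader might infer that no symptomatic non-DILI patient can enter once the diagnosis is known. The AIH patients can, up to 8 weeks from diagnosis. A reader might infer two separate entry windows, but there is one, which closes early for some. A reader might take this to be the trial's key comparison. Statistical Analyses names no key contrast and no visit, the primary endpoint is acquisition of samples and data, and biomarker evaluation is secondary. A reader might also conclude that a large bias is certain, which the protocol gives no figures to show.

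**Conclusion.** The point holds in limited form. For symptomatic controls who enter as suspected cases and are reclassified later, the entry rules make earlier sampling likely, and nothing stated in the protocol aligns or adjusts for it. The direction follows from the eligibility text, given similar referral timing in the two groups. The size does not. It rests on assumed times to alternative diagnosis, entry patterns and marker half-lives, and runs from negligible (0.05 SD, chance 0.06) to dominant (0.75 SD, chance 1.00), with 130 as the upper limit for the control group. This is a risk to the secondary biomarker objective that can be reduced cheaply. It is not evidence that the comparison must fail.

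**What to change.** 1. **Record dates.** For every symptomatic participant, including those later adjudicated non-DILI, record the date of onset or first abnormal liver test and the date of clinical diagnosis, and derive days from onset to each sample. Appendix 1 has no row for these dates, although the separate CRF may. The Data collection section omits DILI-episode information for controls, so make clear that this does not remove onset dates from symptomatic controls.
2. **State the analysis.** In Statistical Analyses, say that the DILI versus symptomatic-control marker comparison is adjusted for days from onset to sample. Add a sensitivity analysis restricted to a common early window, because adjustment extrapolates where few controls were sampled late. Report the unadjusted Visit 1 comparison as secondary.

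**Cost.** This means two dates and one extra covariate. Grading of disease duration already needs the onset date for DILI cases. The adjusted analysis loses no patient for whom the dates are recorded; the restricted one drops late-enrolled DILI cases from that analysis only. Enrolment rules and visits are unchanged.

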Plasma and serum will be prepared from blood samples after collection and stored at -80°C for subsequent analysis of circulating biomarkers identified in other studies. This resource will allow subsequent studies to validate new markers as potential indicators for diseases diagnosis or prognosis.

Whole blood will be collected and stored to be available for future DNA extraction and analysis of genetic biomarkers. Although recent studies have identified some genetic factors for DILI [13], genetic tests are not yet available for DILI. Any findings of genetic tests for these patients will only be revealed some time after the DILI event has resolved so is not likely to be of significant clinical value to their condition and will not be conveyed to the patient.

The total volume of blood taken at one visit will not exceed 80ml.

Stool and Urine samples will also be collected where possible. These will be stored for analysis to investigate urinary biomarkers of disease and for gut microbiome and metabolite analysis.

Any surplus liver tissue available where a liver biopsy is performed as part of clinical care will be collected and stored for research use. This will facilitate analysis of tissue markers and correlation with circulating biomarkers and will enable specific staining to identify clinical features. Extracted RNA will be utilised for expression analysis to investigate possible disease mechanisms.

Similarly where available residual blood from routine clinical testing may be collected for analysis of biomarkers where available.

STUDY DESIGN

Study Configuration:

This is a case-controlled multi-centre study for the collection and storage of biological samples and data (medical, demographic and clinical). We will prospectively develop a cohort of patients with liver injury suspected to be induced by prescription drugs, over-the-counter medications, herbal remedies or dietary supplement intake identified by the participating clinical centres. Each patient will be followed from the identification of hepatotoxicity until normalization of the analytical liver profile.

Coordinating Centres:

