As far as possible, research bloods will be collected at the same time as bloods for clinical care of the patient and visits arranged to coincide with hospital appointments. Preferred visit times are given below but visits outside the times will not be considered as a protocol deviation. Appendix 1 lists the standard clinical care analyses (including ultrasound, viral hepatitis screen, autoantibody screen, haematology and blood chemistry), and research assessments which may be carried out at each visit.

Patients with suspected DILI who are recruited and subsequently found to not have drugrelated injury will continue to provide further samples for this research (as detailed in the PIS). Visit 2 will be 7 ± 8 days from Visit 1. Visit 3 will be 30 ± 20 days after the Visit 1

For those who are in-patients (hospitalised at the time of acute DILI) we will secure additional data and samples on up to 2 further time points (termed visit 1B and Visit 1C) during the period of the patient's hospitalization. In such cases samples will be collected as part of clinical care and additional samples collected for research purposes. If patients continue to have DILI symptoms with raised liver enzymes (i.e. ALT, ALP or total bilirubin levels exceeding the normal range) at Visit 3, a further visit after approximately 3 months (Visit 4) will be arranged to collect the same set of samples. If enzymes remain above normal at this visit, samples will be collected again approximately 3 months later at Visit 5.

Sampling Schedule

- At each visit a delegated member of the research team will collect:
- Up to 80ml of blood. See most recent study presentation and/or sample collection SOP for details.
- Up to **50 ml of urine** (if possible)
- A Stool sample will also be collected (if possible).

Patients may be consented and samples collected at their home if appropriate and with permission of the PI. Nursing staff would be required to follow their Trust's lone working policy and code of practice.

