Appendix 1. Overview of Patient assessment schedule

*Autoantibodies: antinuclear (ANA), antismooth muscle (ASMA), antimitochondrial (AMA) and liver kidney microsomal type 1 (LKM-1)

**Repeat autoantibody screening if positive in week 1

[#] For 'past DILI' patient group and control groups there will be just a single visit, visit 1 -clinical blood tests will not be done.

[§]Only if patient is hospitalized, ^{§§}Only if patient has elevated liver profile values at visit 3, ^{§§§}Only patients with elevated liver profile values at previous visit (visit 4) Appendix 2 Histopathological terms to be used for liver biopsy reports in patients with suspected drug-induced hepatotoxicity.

CODE	DESCRIPTION
1	HEPATOCELLULAR NECROSIS
11	FOCAL NECROSIS
12	BRIDGE NECROSIS
13	ZONAL NECROSIS
14	MASSIVE NECROSIS
2	STEATOSIS / FATTY LIVER
21	ACUTE STEATOTIC CHANGES
22	STEATOHEPATITIS (NASH)
3	GRANULOMATOUS REACTION
4	ACUTE COLESTASIS
41	CHOLESTASIS WITHOUT HEPATITIS
42	CHOLESTASIS WITH HEPATITIS
43	CHOLESTASIS WITH DUCTAL LESION
5	CHRONIC CHOLESTASIS
51	PROLONGED CHOLESTASIS
52	DUCTOPENIA ("VANISHING BILE DUCT SYNDROME")
53	SCLEROSING CHOLANGITIS
6	CHRONIC HEPATITIS
61	CHRONIC ACTIVE HEPATITIS
62	HEPATIC FIBROSIS AND CIRRHOSIS
7	VASCULAR ALTERATIONS
71	SINUSOIDAL DILATATION (FLARING) AND PELIOSIS
72	NON-CIRRHOTIC PORTAL HYPERTENTION
73	OBSTRUCTION TO THE VENOUS HEPATIC FLOW (Budd-Chiari
74	OTHERS
8	HEPATIC TUMORS
81	HEPATOCELLULAR ADENOMA
82	HEPATOCELLULAR CARCINOMA
83	OTHER CARCINOMAS
84	ANGIOSARCOMA
9	UNSPECIFIC CHANGES

Appendix 3

Drug-induced Liver Injury

Introduction to **DILI**

- DILI is an unexpected injury to the liver that can be caused by prescribed medications, over-the-counter medications, recreational drugs and supplements.
- Some drugs such as paracetamol are known to be harmful to the liver in high doses but other drugs, taken at a normal dose can unpredictably damage the liver of certain people.
- DILI is a rare, unpredictable disease and it is not known why certain individuals are more likely to develop drug-induced liver injury than others. This can be life-threatening.
- · Specific genetic risk factors can contribute to individual susceptibility but they do not fully explain why people get DILI.

Study Aims

To create a unique International Biobank resource to enable research into the causes and characteristics of drug-induced liver injury (DILI) so that new, non-invasive diagnostic tests can be developed

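### The Visit 4 trigger in Study Procedures adds a symptom condition that Appendix 1 does not have, so late research samples could be lost for symptom-free patients with raised liver values

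*Protocol*

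**What the plan says.** The Visit 4 rule stands in two places in the Protocol.

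- **Study Procedures, Sample Collection (suspected DILI patients).** The condition is "If patients continue to have DILI symptoms with raised liver enzymes" at Visit 3. A bracket explains the enzymes as ALT, ALP or total bilirubin above the normal range. If the condition is met, "a further visit after approximately 3 months (Visit 4) will be arranged to collect the same set of samples".
- **Appendix 1, footnote to Visit 4.** "Only if patient has elevated liver profile values at visit 3".

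The Visit 5 rule also stands in both places, without symptoms in either. Study Procedures has "If enzymes remain above normal at this visit, samples will be collected again approximately 3 months later at Visit 5", and the Appendix 1 footnote has "Only patients with elevated liver profile values at previous visit (visit 4").

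Two general follow-up rules bear on the point. Study Configuration and Enrolment both say: "Each patient will be followed from the identification of hepatotoxicity until normalization of the analytical liver profile". The Follow-up paragraph of Study Population sets clinical follow-up "until the event resolves or 12 weeks after the first event whichever occurs later". Neither mentions symptoms.

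**The concern.** Of all the rules that decide how long a patient is followed or sampled, only the Visit 4 sentence in Study Procedures names symptoms. Taken literally it needs two things at Visit 3: continuing symptoms and raised values. A patient who feels well but still has a raised ALT, ALP or bilirubin meets the Appendix 1 condition and fails this one. Because Visit 5 depends on the values at Visit 4, that patient would lose both visits.

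One objective in the Study Summary is to collect samples over the whole course of the event, at onset and during follow-up. If some sites apply the literal wording, the blood, urine and stool taken at about 3 and 6 months would come from patients selected on symptoms, and the selection would vary by site. Symptoms also enter the severity grading under Secondary endpoints, where symptomatic hepatitis is enough for the Moderate grade. The selection would therefore be related to the severity that the planned marker panel is meant to assess. Samples not taken at the time cannot be recovered later.

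**Working it through.** **1. The rules side by side**

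| Rule | Place in Protocol | Symptoms required? | Raised liver values required? |
|---|---|---|---|
| Visit 4 | Study Procedures | Yes, as worded | Yes |
| Visit 4 | Appendix 1 footnote | No | Yes |
| Visit 5 | Study Procedures | No | Yes |
| Visit 5 | Appendix 1 footnote | No | Yes |
| Follow-up to normalisation | Study Configuration; Enrolment | No | Until normal |
| Clinical follow-up | Study Population, Follow-up | No | Until resolved or 12 weeks, whichever is later |

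The two Visit 4 texts agree for a patient with both symptoms and raised values, and for a patient with normal values. They part only for raised values without symptoms.

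**2. Can such a patient exist?** Yes. The entry thresholds are laboratory values. The other criteria are drug exposure and clinical suspicion, and no symptom is required. The severity grading treats symptomatic hepatitis as separate from the bilirubin threshold, so a case graded Mild has no symptomatic hepatitis.

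**3. What would be lost per patient?** 

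- Outpatient: Visits 1 to 5 give up to 5 occasions; 5 − 2 = 3.
- Inpatient with Visits 1B and 1C: up to 7 occasions; 7 − 2 = 5.

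**4. When would the lost samples have been taken?** Appendix 1 gives windows from enrolment. Study Procedures instead places Visits 4 and 5 about 3 months after the previous visit, taken here as 91 days (my assumption). Enrolment may follow diagnosis by up to 8 weeks, so a lag of 0 to 56 days is added for time from diagnosis.

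| Visit | From enrolment, Appendix 1 | From enrolment, Study Procedures | From diagnosis, Appendix 1 | From diagnosis, Study Procedures |
|---|---|---|---|---|
| 3 | 30 ± 20 = Day 10–50 | Day 10–50 | Day 10 to 50 + 56 = 106 | Day 10–106 |
| 4 | 90 ± 30 = Day 60–120 | 10 + 91 to 50 + 91 = Day 101–141 | Day 60 to 120 + 56 = 176 | Day 101 to 141 + 56 = 197 |
| 5 | 180 ± 90 = Day 90–270 | 101 + 91 to 141 + 91 = Day 192–232 | Day 90 to 270 + 56 = 326 | Day 192 to 232 + 56 = 288 |

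These are preferred times, not limits. Under the literal reading the last scheduled research sample is Visit 3, at Day 10–50 from enrolment. The nominal Visits 4 and 5 (Days 90 and 180) lie near the 3-month and 6-month marks that define persistent DILI.

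**5. How many patients?** The Protocol gives no share of patients who are symptom-free with raised values at Visit 3, so the number affected cannot be stated.

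**The case against.** The strongest reply is that the sentence is loosely worded and the protocol resolves it. Suspected cases as a group are labelled symptomatic in the Study Summary and under Primary endpoint, and controls are described in Study Population as free of DILI symptoms. On that usage the phrase means only that the liver event is still present. The bracket supplies the only criterion a site can test, since no list of DILI symptoms is given. The next sentence carries the enzyme criterion forward alone, and the section refers sites to Appendix 1. Nor is there a strict contradiction: Study Procedures says when Visit 4 is arranged, the footnote says when it may not be, and sampling a symptom-free patient with raised values breaches neither. The section also refers to a visit diagram that is not reproduced in the text available here and may state the trigger.

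Much of this stands. The intended rule is very probably biochemical, and the effect is confined to optional visits. Persistence can still be graded from clinical follow-up, and "residual blood from routine clinical testing may be collected for analysis of biomarkers where available".

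It does not remove the point. The Informed Consent section uses the same phrase for acute complaints that bring patients to emergency departments, so the literal reading has support in the document. Permission to sample is not an instruction to do so, and the instruction is the sentence that names symptoms. That sentence also fits poorly with cases later found not to be DILI, whose sampling is meant to continue on the same terms as for confirmed cases.

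**Conclusion.** The concern holds as a minor error of wording in an operative sampling rule. Followed as written, Study Procedures would end scheduled research sampling at Visit 3 for symptom-free patients whose liver values are still raised, whereas Appendix 1 provides for Visit 4 and, if values stay raised, Visit 5. The loss is at most 2 optional occasions per affected patient.

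The harm depends on at least some sites reading the sentence literally, which is possible but not shown, and on a share of patients that the documents do not give. The 91-day month conversion affects only the illustrative visit days. The primary endpoint counts and clinical follow-up do not change under either reading.

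**What to change.** In the Visit 4 sentence of Study Procedures, delete the three words *DILI symptoms with* and leave the rest as it is. Visit 4 is then triggered by ALT, ALP or total bilirubin above the normal range at Visit 3, as in Appendix 1 and in line with the Visit 5 rule. The wording also applies unchanged to cases later judged not to be DILI. It would help to ask sites which rule they have applied, so that gaps in the late samples can be interpreted.

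The cost is up to two further sampling visits per affected patient, with at most 80 ml of blood each (2 × 80 = 160 ml). Appendix 1 already foresees these visits, and they are to coincide with routine appointments as far as possible.
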